Patients must be able to read and comprehend English, except French patients from CCTG institutions. (See [§ 3.2.22](#))

Schema

* Regional Nodes will include axilla (Levels I, II, III), supraclavicular fossa and internal mammary nodes. If an axillary dissection has been performed, RT will only be directed to the un-dissected axilla.

** Patients will be stratified before randomization for immediate versus delayed and autologous versus implant only reconstruction. All reconstruction must be completed before radiation to be classified as immediate and autologous reconstruction is autologous tissue +/- implant.

All patients will undergo reconstruction of the breast; either before or after radiation, but it must be completed within 18 months after finishing radiation therapy, unless medically contraindicated.

Patients will be followed until 15 years after completion of radiation therapy or until death, whichever comes first ([§11.3](#))

Please refer to the full protocol text for a complete description of the eligibility criteria and treatment plan.

There is no surgical credentialing required for participation on this study.

Radiation therapy requires credentialing and submission of patient plans for review. See Sections [7.5](#) and [14.0](#) for more detail.

Table of Contents

Section	Page
1.0 BACKGROUND	8
1.1 Rationale for the Study	8
1.2 Baseline Toxicity from PMRT.....	9
1.3 Altered Fractionation in Breast Cancer.....	11
1.4 Patient Satisfaction and Well-being as Patient Reported Outcomes (PROs).....	12
1.5 Photographic Cosmetic Assessment	14
1.6 Study Hypotheses	14
2.0 OBJECTIVES	14
2.1 Primary Objective	14
2.2 Secondary Objectives.....	14
2.3 Photographic Cosmetic Assessment	15
2.4 Lymphedema Assessment.....	15
2.5 Patient Reported Outcomes (PRO) Objectives	15
2.6 Economic Analysis	15
2.7 Correlative Science Objectives	15
3.0 PATIENT SELECTION.....	16
3.1 On-Study Guidelines.....	16
3.2 Eligibility Criteria	17
4.0 PATIENT REGISTRATION.....	19
4.1 Investigator and Research Associate registration with CTEP.....	19
4.2 CTSU Site Registration Procedures	20
4.3 Patient Registration Requirements.....	22
4.4 Patient Registration/Randomization Procedures.....	22
4.5 Registration to Correlative and Companion Studies.....	23
4.6 Stratification Factors and Treatment Assignments	23
5.0 STUDY CALENDAR.....	25
6.0 DATA AND SPECIMEN SUBMISSION.....	26
6.1 Data Collection and Submission	26
6.2 Specimen collection and submission	28

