11.3 Follow-up

11.3.1 Duration of follow up

Patients who complete radiation therapy and breast reconstruction-will be followed as outlined in Section 5.0 until disease recurrence, contralateral breast cancer, or a non-breast second primary cancer; or until an alternative treatment is given for up to 15 years after the end of radiation therapy. All follow up (including survival) done after 5 years will be gathered by record review only.

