11.3.2 Follow up for patients who do not complete radiation and breast reconstruction

Patients who complete radiation per protocol, but who do not complete reconstruction will also be followed as outlined in [Section 5.0](#) until disease recurrence, contralateral breast cancer, or a non-breast second primary cancer; or until an alternative treatment is given for up to 15 years

after the end of radiation therapy. All follow up (including survival) done after 5 years will be gathered by record review only.

Patients who experience disease recurrence, contralateral breast cancer, or a non-breast second primary cancer, or alternative treatment will discontinue protocol therapy and no further follow up will be required.

11.4 Managing Ineligible Patients and Registered Patients Who Never Receive Protocol Intervention

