12.4 Supplementary/Secondary Analysis Plans

12.4.1 Secondary Objectives

Incidence of acute and late radiation complications based on CTCAE 4.0 toxicity. The proportion of patients with acute or late radiation complications, will be estimated separately by treatment arm and will be compared across the two arms using two-sample test of proportions (Z test) with a two-sided alternative.

Local and local regional recurrence rate: The cumulative incidence of local and local regional recurrence will be estimated separately by treatment arm using the cumulative incidence function treating death as the competing risk and will be compared using Gray's test. In addition, local and local regional recurrence free survival will be summarized for each arm using the Kaplan-Meier estimators, and will be compared using a log rank test.

Reconstruction complication rates based on reconstruction method (autologous +/- implant vs. implant only) and timing of reconstruction received (immediate vs. intent for delayed): Between-arm differences in reconstruction complication rates will be assessed separately within each of the six subgroups based on type and timing of reconstruction. Between-arm differences in complication rates will also be assessed within the two broader subgroups of patients who receive implant only and those who receive autologous based reconstruction. Within each subgroup, the comparison will be done using a two-sample Z test of proportions with a two-sided alternative as described for the primary analysis in Section 12.3.2.

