In addition to using them to estimate direct costs, the health care utilization measures (number of outpatient visits to the radiation oncologist, medical oncologist, surgeon who performed mastectomy, plastic surgeon, physical therapist; the number of visits to the emergency room, the number of hospital admissions, the days per each hospital admission, and the number of surgical procedures to breast reconstruction) will be compared (separately) across the two dosing arms. Given that these outcomes are counts, appropriate count regression models (e.g., poisson regression, negative binomial regression or zero-inflated negative binomial regression) will be used to account for any residual imbalance between the study arms following randomization.

EQ-5D survey results for the baseline and follow-up will be presented in three ways: (i) the descriptive system on the 5 dimensions will reflect the patients general health profile; (ii) EQ-VAS will represent patients' self-reported health status; and (iii) the summary measure of generic health status in terms of EQ-5D-3L index value. In order to obtain the last measure, EQ-5D responses representing specific health state will be converted to a single index value using the EQ-5D-3L value sets for the U.S. This, along with the survival data, will then be used to estimate the effectiveness measure in our cost-effectiveness analysis, that is, quality adjusted life year or QALY. Mean QALYs between interventions will be compared using two-sided t-test. Cost-effectiveness will be assessed and compared in terms of incremental cost-effectiveness ratio or ICER, that is, US dollars per QALY between the interventions. Costs associated with each of the interventions will be estimated. For healthcare utilizations mentioned above, costs will be imputed from the literature. Extensive sensitivity analyses will be conducted to document sensitivity of the final results to any of the imputed cost parameters.

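### Section 11.3 ends follow-up at any recurrence or second cancer, against the schema, and section 12.4.1 names only death as competing, so distant relapses are censored informatively in the recurrence analysis

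*Combined protocol and SAP*

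**What the plan says.** **How long patients are followed.** The schema states: "Patients will be followed until 15 years after completion of radiation therapy or until death, whichever comes first", and refers to section 11.3. Section 11.3.1, for patients who complete radiation and reconstruction, runs follow-up "until disease recurrence, contralateral breast cancer, or a non-breast second primary cancer; or until an alternative treatment is given for up to 15 years". Section 11.3.2 gives the same end points for patients who complete radiation but not reconstruction, and adds that patients with these events "will discontinue protocol therapy and no further follow up will be required". Sections 11.4.3 (withdrawal after starting treatment) and 11.5 (extraordinary circumstances) use the same terminating events.

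**What is analysed.** Objective 2.2.2 is the local and local-regional recurrence rate. Section 10.3 classes distant recurrence separately, so a distant relapse is not an event for this endpoint. Section 12.4.1 uses a "cumulative incidence function treating death as the competing risk", compared by Gray's test. In addition, "local and local regional recurrence free survival will be summarized for each arm using the Kaplan-Meier estimators", compared by a log-rank test. Neither the events nor the censoring rule for recurrence-free survival is given, and nothing is said about patients whose follow-up ended at a distant recurrence or second cancer.

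**Where else the data are used.** In section 12.4.5 the EQ-5D index, "along with the survival data, will then be used to estimate the effectiveness measure" (the QALY). The study calendar schedules recurrence, cardiac and plexopathy review at 10 and 15 years, and section 5.0 says that data after year 5, survival status included, come from records only.

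**The concern.** A patient with a distant relapse reaches the end of required follow-up without having had a local-regional event. Since death is the only competing event named and no other rule is given, the default is to censor her. Censoring assumes that she has the same future risk as patients still under observation. After a distant relapse that is not credible: her risk of death is much higher, and the death that the analysis wants to treat as competing need no longer be observed. Later local-regional recurrences are missed too. A second cancer has the same effect on follow-up.

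Section 1.6 hypothesises a similar recurrence rate with the shorter schedule, so the arm-level recurrence estimates will be read as evidence on oncologic safety. Section 12.5 also relates local-regional recurrence to genotype. The late cardiac and plexopathy review loses the same patients.

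**Working it through.** **Plan figure.** The documents give no sample size, power or event count for the recurrence analysis, so there is none to reproduce. The primary-endpoint size in 12.2 does reproduce: (1.960 + 1.282)² × 2 × 0.25 × 0.75 / 0.10² gives 395 per arm against 396 stated. The present point does not depend on it.

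**Step 1: first-event incidence.** Let λ be the local-regional and δ the distant hazard, both constant. The hazards are assumptions: λ = 0.006 per year, δ = 0.02 or 0.03 per year. Section 1.1 allows a plausibility check, though from older cohorts. A local recurrence of 4% at 10 years implies −ln(0.96)/10 = 0.0041; a locoregional recurrence of 6% at 5 years implies −ln(0.94)/5 = 0.0124; a systemic disease-free survival of 48% at 20 years implies −ln(0.48)/20 = 0.037. The assumed values lie within or below these.

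- Distant recurrence as competing: F(t) = λ/(λ+δ) × [1 − exp(−(λ+δ)t)]
- Distant recurrence censored: C(t) = 1 − exp(−λt)

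| δ | t | F(t) | C(t) | Gap (points) | Ratio |
|---|---|---|---|---|---|
| 0.03 | 10 y | 0.006/0.036 × (1 − e^−0.36) = 5.039% | 1 − e^−0.06 = 5.824% | 0.78 | 1.156 |
| 0.02 | 10 y | 0.006/0.026 × (1 − e^−0.26) = 5.283% | 5.824% | 0.54 | 1.102 |
| 0.03 | 5 y | 0.006/0.036 × (1 − e^−0.18) = 2.745% | 1 − e^−0.03 = 2.955% | 0.21 | 1.08 |
| 0.02 | 5 y | 0.006/0.026 × (1 − e^−0.13) = 2.813% | 2.955% | 0.14 | 1.05 |

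The share leaving follow-up for distant recurrence by 10 years is δ/(λ+δ) × [1 − exp(−10(λ+δ))]: 25% at δ = 0.03 and 18% at δ = 0.02.

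**Step 2: wider range, with death included.** Further assumptions: δ from 0.015 to 0.037 per year, death without recurrence μ = 0.005, death after distant recurrence ν = 0.30, and a local-regional hazard after distant recurrence of k = 0 to 3 times that before. At 10 years:

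| | λ = 0.0041 | λ = 0.0124 |
|---|---|---|
| Censored at distant recurrence (11.3 and 12.4.1 as written) | 3.9% | 11.4% |
| First event, distant recurrence competing | 3.3–3.6% | 9.6–10.6% |
| Any time, follow-up continued, death competing | 3.3–4.1% | 9.6–11.9% |

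Against the first-event quantity the overstatement is about 0.3 to 1.8 points. Against recurrence at any time the error runs from about −0.5 to +1.8 points, so its sign is not fixed.

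**Step 3: recurrence-free survival, taking death as an event.** With patients censored at distant recurrence and later deaths unseen, the estimate is exp(−(λ+μ)t). With those deaths captured, write a = λ+δ+μ and b = ν+kλ; the value is exp(−at) + δ/(b−a) × [exp(−at) − exp(−bt)]. For λ = 0.0041, δ = 0.015, k = 0, t = 10: a = 0.0241, and 0.786 + 0.0544 × (0.786 − 0.050) = 0.826, against exp(−0.0908) = 0.913. Over the whole range:

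| | As written | Deaths captured | Overstatement |
|---|---|---|---|
| 10 y, λ = 0.0041 | 91.3% | 71–83% | about 9–20 points |
| 10 y, λ = 0.0124 | 84.1% | 65–76% | about 8–19 points |
| 5 y, λ = 0.0041 | 95.6% | 87.6–92.3% | 3.3–8.0 points |
| 5 y, λ = 0.0124 | 91.7% | 83.8–88.6% | 3.1–7.9 points |

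**Step 4: QALYs.** The EQ-5D stops at 24 months and the documents state no QALY horizon, so no effect can be computed. The gap in survival data after recurrence remains.

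**The case against.** The strongest reply is that the schema already promises follow-up to death. If it governs, most of the bias disappears. This stands as a condition, and the sizes above apply only if 11.3 is followed. But four sections say otherwise, and 11.3.2 tells sites expressly that they may stop.

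A second reply is that deaths reach the database anyway: section 9.4 requires reporting of all deaths on study and gives a rule for death from progressive disease, and section 10.3.6 asks for the cause of death. Some deaths may be caught this way, which would shrink the figures in step 3. None of these passages restores the follow-up that 11.3.2 ends. The missing-data section (12.6) is built around patient-reported scores and does not cover this case.

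Four stronger readings are tempting, and the documents do not support them:

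- *That the comparison of arms is biased.* It is biased only if distant recurrence, second cancer or alternative treatment differs by arm. Section 1.1 expects equal effectiveness, and a log-rank comparison of cause-specific local-regional hazards survives this censoring.
- *That local-regional recurrence is overstated whatever is meant by it.* This holds for first events. Section 12.4.1 does not say which quantity is meant, and for recurrence at any time the lost later events pull the other way.
- *That overall survival is a distorted endpoint.* It is not a listed objective. Survival enters through recurrence-free survival, the competing risk and QALYs.
- *That starting therapy for relapse is what ends follow-up as alternative treatment.* Section 11.2 uses that term for treatment replacing protocol radiation, or radiation not per protocol, before or during the treatment period. It is the relapse itself that ends follow-up.

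**Conclusion.** The contradiction between the schema and sections 11.3.1, 11.3.2, 11.4.3 and 11.5 is plain in the text and has to be resolved. If those sections are followed together with 12.4.1, distant relapses and second cancers are censored informatively by default.

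The effect on first-event local-regional incidence is upward and small at 5 years (0.14 to 0.21 points), and about 0.5 to 0.8 points at 10 years under the simple hazards. The wider range reaches 1.8 points at 10 years. The effect on recurrence-free survival is larger, about 8 to 20 points too high at 10 years. That figure assumes that death counts as an event, that no death after distant recurrence is captured, and that mortality after relapse is 0.30 per year.

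All hazards are illustrative; the documents give none for this trial. The defect concerns arm-level estimates of secondary endpoints and the survival input to QALYs. It leaves the primary endpoint's design figures untouched.

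**What to change.** 1. Reconcile 11.3.1, 11.3.2, 11.4.3 and 11.5 with the schema, so that local-regional recurrence, survival status, and the scheduled cardiac and plexopathy record review continue to 15 years or death after a recurrence or second cancer. The cost is a modest record-review workload; data after year 5 already come from records only. Data not collected now may be hard to recover later.
2. In 12.4.1 choose one primary estimand:
   - first-event local-regional recurrence, with distant recurrence, second cancer and death as competing events. This is required if follow-up still stops at those events, and it costs only wording.
   - local-regional recurrence at any time, with death competing. This is valid only if follow-up continues as in item 1.
3. State which events count in recurrence-free survival, and the censoring rule that goes with the choice in item 2. If death is an event, survival status after distant recurrence must be collected. State the QALY horizon and how survival after recurrence enters it.
4. As a reporting addition only, give the arm difference in 5-year cumulative incidence with a 95% confidence interval beside Gray's test. It does not repair the censoring, but a non-significant test alone would not show similar recurrence rates.

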12.4.2 Photographic Cosmetic Assessment

Reconstructed breast photographic cosmetic scores 24 months after radiation with hypofractionated radiation compared to standard fractionation: Two year photographic cosmetic scores will be summarized by treatment arm and will be compared across the treatment arms using a Wilcoxon rank-sum test with a two-sided alternative. The proportions of patients with poor global cosmetic score (defined as a cosmetic score of 3: poor or large difference) at 24 months after radiation will be summarized separately by treatment arm and will be compared using a two-sample test of proportions with a two-sided alternative.

Reconstructed breast photographic cosmetic scores 24 months after radiation based on the method and timing of reconstruction received: Two year photographic cosmetic scores and the proportions of patients with poor global cosmetic score will be assessed separately by timing and method of reconstruction subgroups using similar method described above.

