1.5 Photographic Cosmetic Assessment

There are no validated photographic assessment tools in patients with breast reconstruction. The EORTC Breast Cosmetic Rating system is a digital photographic method that has been utilized in prior radiation studies and shown to be reliable and valid in detecting effects of radiation morbidity. [45-47] This method compares the radiated breast with the contralateral untreated side and evaluates: Size, shape, location of the areola/nipple, appearance of the surgical scar, skin pigmentation changes, presence of telangiectasia and a global cosmetic score based on all of the factors. Characteristics are graded on a four-point scale: 0, excellent or no difference; 1, good or small difference; 2, fair or moderate difference; and 3, poor or large difference.

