7.1 Surgical Management

7.1.1 Mastectomy

Surgery may be completed as a total, simple, skin sparing, nipple sparing or modified radical mastectomy.

Margins should be negative, defined as no tumor on ink. A focally positive deep margin will be considered a negative margin if the deep margin is the pectoralis fascia and the pectoralis fascia was noted as removed in the operative description or pathology report. This is provided there is no evidence of pectoralis fascia invasion by imaging or pathological evaluation.

Lymph nodes must be evaluated by sentinel node biopsy or axillary dissection. The majority of these patients will have positive lymph nodes in order to qualify for enrollment. This protocol does not stipulate sentinel node versus axillary dissection, but does require lymph node management per standard of care. Patients will be recorded as having undergone a sentinel node only procedure or an axillary dissection. A sentinel node procedure will be considered an axillary dissection if more than 5 lymph nodes are removed.

Mastectomy and nodal evaluation must be completed within 56 days of the completion of neoadjuvant chemotherapy. Radiation must start per section 7.0.

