10.6 Photographic Cosmetic Assessment

An important outcome of this study is the cosmetic outcome of hypofractionated radiation versus conventional radiation and the risks of late radiation morbidity. These side effects include telangiectasia, breast fibrosis, scar retraction and skin pigmentation changes, which may all affect the cosmetic result. As this is not a blinded study, cosmetic assessment will be by digital photography reviewed by a Central Adjudication Committee unaware of treatment allocation evaluating late radiation morbidity.

Confidential bilateral digital photographs (excluding the face) will be taken with a digital camera:

- 1) Standing, anterior photo to show both breasts with the arms at 45° from the body and
- 2) Close up of treated area to show the surgical scar and surrounding reconstructed tissue at 24 months post radiation.

Photographs will be captured of both breast/reconstructed chest walls at the following time points:

- Before radiation, only for patients with immediate reconstruction
- 24 months after the completion of radiation for all patients.

Photographs of both breasts will be collected as above and reviewed by a blinded Central Adjudication Committee according to the modified EORTC Cosmetic Rating System. Study participants will be identified only by study ID number of their photographs to ensure confidentiality. De-identified photographs will be submitted to IROC Rhode Island where they will be prepared for review and archived with the patient record. See section 6.3 for instructions for submission of photographs. The review process has been used extensively in the past, including in the recent Canadian RAPID study of partial breast radiation. The treated breast will be compared to the intact opposite breast or contralateral reconstructed chest wall. For patients who have their final reconstruction performed prior to starting radiation, there will also be pre-radiation photographs taken. Patients who develop an ipsilateral breast cancer or lymph node recurrence before the 24 month photography assessment will not be assessed. We will use the modified EORTC digital photographic method used in the Canadian RAPID trial. This approach has been shown to be reliable in intact breast patients and is validated in detecting the effects of radiation morbidity. [45-47]. Unfortunately, there are no validated photographic assessment tools in reconstructed breast patients.

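### The overall comparison of 24-month photographic cosmetic scores uses neither the stratification factors nor the pre-radiation photographs the trial collects, and so gives up precision

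*Combined protocol and SAP*

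**What the plan says.** The instrument (Section 1.5): "This method compares the radiated breast with the contralateral untreated side and evaluates: Size, shape, location of the areola/nipple, appearance of the surgical scar". The list continues: "skin pigmentation changes, presence of telangiectasia and a global cosmetic score based on all of the factors". Each characteristic is graded from 0 (excellent or no difference) to 3 (poor or large difference).

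The comparator (Section 10.6): "The treated breast will be compared to the intact opposite breast or contralateral reconstructed chest wall".

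The surgery (Section 7.1.1): "Surgery may be completed as a total, simple, skin sparing, nipple sparing or modified radical mastectomy". Section 7.2 lists six combinations of reconstruction type and timing.

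The photographs (Section 10.6): all patients are photographed at 24 months. "For patients who have their final reconstruction performed prior to starting radiation, there will also be pre-radiation photographs taken". Section 5.0 (note D) and Section 6.4 also schedule this earlier photograph. The images are "reviewed by a Central Adjudication Committee unaware of treatment allocation evaluating late radiation morbidity".

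The analysis (Section 12.4.2): "Two year photographic cosmetic scores will be summarized by treatment arm and will be compared across the treatment arms using a Wilcoxon rank-sum test", two-sided, plus a two-sample test of the proportions with a global score of 3. Both are repeated by timing and method of reconstruction. The pre-radiation photographs are not mentioned there or in Objectives 2.3.1 and 2.3.2.

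The allocation (Section 4.6): dynamic allocation balanced on planned reconstruction type (autologous with or without implant, or implant only) and timing (immediate or delayed).

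**The concern.** Several scored items can differ between the two sides before any radiation is given, depending on whether the nipple was kept, how the breast was rebuilt, and whether the other side is intact or reconstructed. That variation is present in both arms and adds spread to the score. Two sources of information could absorb part of it: the factors on which allocation is balanced and, in one subset, a photograph of the same reconstruction before radiation. The overall arm comparison ignores both.

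Section 1.6 hypothesises better cosmesis with hypofractionation, so this is a comparison looking for a difference, and lost sensitivity counts against it. A null result from a noisier test is easier to misread as evidence of no difference.

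**Working it through.** **Consistency within the plan**

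- Section 12.4.3 analyses arm volume as change from the pre-radiation value.
- Section 12.4.4 analyses LBCQ and BLE scores at 24 months relative to pre-radiation.
- Section 12.3.2 adds a sensitivity analysis of the primary endpoint stratified by reconstruction timing and type.
- Section 12.4.2 has no baseline term and no stratified overall comparison. Separate subgroup results do not combine into one stratified test.

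**Is there a planned figure to reproduce?** Not for the photographic score: the documents give no power, standard deviation or effect size for it. The only sample size is that for the primary endpoint (Section 12.2). With 25% in each arm, a margin of 10 points, one-sided 0.025 and 90% power:

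n per arm = (1.960 + 1.282)² × 2 × 0.25 × 0.75 / 0.10² ≈ 394.0, rounded up to 395.

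The plan states 396 per arm (792 in total). That figure is sound and is used below only for scale. Fewer patients will be scored in practice, because Section 10.6 drops those with an ipsilateral breast or nodal recurrence before 24 months.

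**Assumed inputs**

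- r, the correlation of the pre-radiation and 24-month scores: 0.3, 0.5, 0.7.
- f, the share of patients with a pre-radiation photograph: 10%, 25%, 50%.
- Equal unadjusted variance and a common arm effect in patients with and without the photograph.
- A linear-model approximation to an ordinal score.

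**Formulas**

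- Within the subset, variance removed = r².
- Over all patients, relative information I = f/(1 − r²) + (1 − f), and variance removed = 1 − 1/I.
- Example with f = 0.25 and r = 0.5: I = 0.25/0.75 + 0.75 = 1.083, so 1 − 1/1.083 = 7.7%.

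| Variance removed | r = 0.3 | r = 0.5 | r = 0.7 |
|---|---|---|---|
| Within the subset | 9% | 25% | 49% |
| All patients, f = 10% | 1.0% | 3.2% | 8.8% |
| All patients, f = 25% | 2.4% | 7.7% | 19.4% |
| All patients, f = 50% | 4.7% | 14.3% | 32.5% |

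**In detectable differences** (396 per arm, two-sided 0.05, 80% power). Unadjusted: (1.96 + 0.84) × √(2/396) = 0.199 SD. Dividing by √I for r from 0.3 to 0.7 gives:

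- f = 10%: 0.198 to 0.190 SD
- f = 25%: 0.197 to 0.179 SD
- f = 50%: 0.194 to 0.164 SD

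These figures cover the baseline score only. The further gain from stratifying by planned type and timing cannot be sized, because the documents do not say how strongly those factors predict the score.

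**The case against.** The strongest case for the plan as written has four parts.

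- *Section 12.4.2 answers its objective.* Objective 2.3.1 asks for a between-arm comparison of scores at 24 months, not of change, and allocation is balanced on the main surgical factors. This stands: the test is valid and unbiased.
- *Surgical variation is already examined.* The scores are also analysed by timing and method of reconstruction. This stands in part, since those are separate subgroup analyses and the overall test remains unstratified.
- *The baseline photographs are not thrown away.* Section 10.6 lists the pre-radiation time point and then sends the photographs to the blinded committee, which is to score them once all are collected. This also stands: scoring appears to be planned, and what is missing is a stated use of the result.
- *Adjustment can do harm.* Delayed reconstruction may be completed up to 18 months after radiation, and contralateral revision is treated as routine. The reconstruction received and the state of the other side at 24 months can therefore be influenced by arm, and adjusting for them could remove part of the effect. This stands in full and limits the fix.

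A reader might also infer that the score largely measures surgery, or that the early photographs were taken in order to isolate radiation change. The documents support neither: no variance share is given, pigmentation and telangiectasia are scored too, and no purpose is stated for those photographs.

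**Conclusion.** The point holds as a loss of precision on a secondary endpoint with no stated power. There is no bias. The overall comparison leaves out a baseline of the same outcome and the factors used in allocation, although the plan uses such information for other endpoints.

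The size depends on two quantities the documents do not give: the correlation and the share of patients with a pre-radiation photograph. Over the assumed ranges, the variance reduction is 9% to 49% within the subset, and about 1–9%, 2–19% or 5–33% over all patients at shares of 10%, 25% or 50%. At the low end the gain is negligible.

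Two stronger readings should be resisted. The subset figures equal 1/(1 − r²) − 1, or about 10%, 33% and 96% more patients, but only in that subset and not in the trial. Nor is the proportion scoring 3 uninterpretable: as a randomised contrast it is meaningful, though surgical variation common to both arms may dilute it.

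**What to change.** In Section 12.4.2:

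1. Make the main analysis of the 24-month global score a proportional-odds model with arm, stratified by the randomisation factors of Section 4.6 (planned reconstruction type and timing). A van Elteren test with the same strata is an alternative, but it does not use the baseline score.
2. In the proportional-odds model, adjust for the blinded pre-radiation score where one exists, with a separate term or indicator for patients without one. Under Section 4.6, immediate reconstruction is complete at randomisation, so apart from photographs that were missed this indicator should largely follow the timing stratum.
3. Use only covariate values fixed before radiation. Do not adjust for reconstruction or contralateral status as received after randomisation.
4. State that the panel scores the pre-radiation photographs under the same blinding as the 24-month ones.
5. Keep the unadjusted rank test and the proportion scoring 3 as supportive analyses.

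Align the wording on who is photographed before radiation as well: Section 6.4 refers to completion with final implants, while Section 5.0 (note D) and Section 10.6 refer to final reconstruction without naming implants.

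The cost is analysis-plan wording, a little panel time to score the baseline photographs, and a proportional-odds assumption to check. No new patient data are needed.
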